Data will be collected retrospectively and prospectively to evaluate the long-term outcomes, durability of effect, and real-world treatment patterns following treatment with Cladribine Tablets or placebo among patients with MS who were part of the parent studies. The objectives of this study are all exploratory and for hypothesis generating purposes.

Exploratory Objectives	Endpoints (Outcome Measures)
Primary	

To evaluate long-term mobility after treatment with an investigational medicinal product (IMP); Cladribine (Tablets or placebo) as part of the Phase III ORACLE MS and CLARITY/CLARITY-EXT clinical trials.
	
Proportion of study participants using a wheelchair (defined as unable to walk beyond approximately 5 meters even with aid, essentially restricted to wheelchair; wheels self in standard wheelchair and transfers alone; up and about in wheelchair some 12 hours a day) the majority of the time in the 3 months prior to Study Visit 1 or participants are bedridden any time prior to Study Visit 1 determined via:
 
 1) Expanded Disability Status Score (EDSS) score of 7.0 or higher, or 2) Alternative clinical description data in medical records
Secondary	

To assess the long-term disability status after treatment with IMP as part of the Phase III ORACLE MS and CLARITY/CLARITY-EXT clinical trials for the CLARITY/CLARITY-EXT and ORACLE MS populations.
	
Proportion of study participants with EDSS of 6.0 or higher as determined by EDSS documentation or alternative clinical description in medical records after last IMP from parent study.

To evaluate differences in clinical characteristics between long-term responders and study participants requiring alternate therapies following treatment with IMP for the CLARITY/CLARITY-EXT and ORACLE MS populations.
	
Clinical characteristics^a at Study Visit 1 of long-term responders (defined as study participants who did not demonstrate any evidence of disease reactivation based on Investigator assessment of clinical and imaging outcomes until Year 4 or later following their last dose^b of IMP and who did not receive disease modifying treatment until Year 4 or later following their last dose^b of IMP) compared to those of other study participants who started on alternate therapy less than 4 years following their last dose^b of IMP for the CLARITY/CLARITY-EXT and ORACLE MS populations.

Exploratory Objectives	Endpoints (Outcome Measures)

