To evaluate long-term mobility after treatment with an investigational medicinal product (IMP; Cladribine Tablets or placebo) as part of the Phase III ORACLE MS and CLARITY/CLARITY-EXT clinical trials.	Proportion of study participants using a wheelchair (defined as unable to walk beyond approximately 5 meters even with aid, essentially restricted to wheelchair; wheels self in standard wheelchair and transfers alone; up and about in wheelchair some 12 hours a day) the majority of the time in the 3 months prior to Study Visit 1 (SV1) or participants are bedridden any time prior to SV1, determined via: 1) Expanded Disability Status Scale (EDSS) score of 7.0 or higher), or Alternative clinical description data in medical records.	Section 14.1
Secondary		

Objectives	Endpoints (Outcome Measures)	IAP section
To assess the long-term disability status after treatment with IMP as part of the Phase III ORACLE MS and CLARITY/CLARITY-EXT clinical trials for the CLARITY/CLARITY-EXT and ORACLE MS populations.	Proportion of study participants with EDSS of 6.0 or higher as determined by EDSS documentation or alternative clinical description in medical records after last IMP from parent study.	Section 14.2.1
To evaluate differences in clinical characteristics between long-term responders and study participants requiring alternate therapies following treatment with IMP for the CLARITY/CLARITY-EXT and ORACLE MS populations.	Clinical characteristics ^a at Study Visit 1 of long-term responders (defined as study participants who did not demonstrate any evidence of disease reactivation based on Investigator assessment of clinical and imaging outcomes until Year 4 or later following their last dose ^b of IMP and who did not receive disease modifying treatment until Year 4 or later following their last dose ^b of IMP) compared to those of other study participants who started on alternate therapy less than 4 years following their last dose ^b of IMP for the CLARITY/CLARITY-EXT and ORACLE MS populations.	Section 14.2.2

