6.5 Final Analysis

All analyses described in this IAP will be performed after the final database lock (see Section 14

for further details on analyses) and summarized in final study report. Results of the final analysis will be summarized in a formal study report.

7 Changes to the Planned Analyses in the Clinical Study Protocol

There are no changes to the analyses planned per protocol.

8 Analysis Populations and Subgroups

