To define (b), (c) and (d): If at least 1 dose of Cladribine has been administered after end of Year 1, for CLARITY or CLARITY EXT then the participant will be considered starting the second treatment course (year). If at least 1 dose of Cladribine has been administered during the first year of CLARITY EXT after receiving at least 1 dose during the second treatment course of CLARITY, then the participant will be considered starting the third treatment course (year). Individual parent study datasets will be used.

2. Long-term Responder/Non-responder:

a. Primary definition

- **Long-term Responder:** Study participants not requiring DMD 4 years or later following their last dose of IMP, and who did not demonstrate any evidence of disease reactivation based on Investigator assessment of clinical and imaging outcomes
- **Non-Responder:** Study participants requiring DMD less than 4 years following their last dose of IMP or who demonstrate any evidence of disease reactivation based on Investigator assessment of clinical and imaging outcomes.

Computation rules:

Prior/concomitant medication eCRF page and “physician sequential treatment decision questions” eCRF page question 8 and 9 to be used to identify the date of the DMD received.

4 years after last dose of IMP = Last dose of IMP date + 4*365.25 days

Evidence of disease reactivation will be defined by either:

- a) MRI lesions: new T1 lesion or new T2 lesion reported
- b) New Relapse reported
- c) EDSS worsening defined as an EDSS score increase of at least 1 point between 2 consecutive visits of at most 365 days (if 2 consecutive EDSS assessments are separated by more than 365 days then EDSS cannot be used in the criteria and will be considered as missing/not reported).

New relapse, MRI lesions and EDSS worsening will be identified utilizing dates in parent studies for the period between last dose of IMP and end of parent study.

For the period following the end of the parent study until SV1 of Classic study the following source data will be used:

- 1) MRI lesion by the eCRF “frequency stable patient monitoring questions” (fspmq) page,

Q4/Q3. If Q4 is answered “yes” the date will be taken from Q3 and determined if the MRI lesion is before the 4 years since last IMP.

- 2) New relapse will be identified using the eCRF “MS Relapse history” page(hxrelap) Q2.2.
- 3) The EDSS worsening by the eCRF “expanded disability status scale (edssr) for retro data” page.

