All partial dates will be imputed as described in Section 9.5.

Different scenarios considering missing/not collected data are provided in the table below:

DMD required	MRI new lesion	New Relapse	EDSS worsening	Responder (Yes/No/ND)
All are missing				ND
At least one is Yes (with or without missing)				No
All are N (with no missing)				Yes
All are N (with at least one missing)				ND

ND=Not determined

b. Definition B (sensitivity):

- **Long-term Responder:** Study participants not requiring DMD 4 years or later following their last dose of IMP.
- **Non-Responder:** Study participants requiring DMD less than 4 years following their last dose of IMP.

c. Definition C (sensitivity)

- **Long-term Responder:** Study participants who did not demonstrate any evidence of disease reactivation based on Investigator assessment of clinical and imaging outcomes 4 years following the last dose of IMP.
- **Non-Responder:** Study participants who demonstrate any evidence of disease reactivation based on Investigator assessment of clinical and imaging outcomes 4 years following the last dose of IMP.

d. Definition D (sensitivity)

- **Long-term Responder:** Study participants who did not demonstrate any evidence of disease reactivation based on Investigator assessment of clinical outcomes 4 years following the last dose of IMP.

- **Non-Responder:** Study participants who demonstrate any evidence of disease reactivation based on Investigator assessment of clinical outcomes 4 years following the last dose of IMP.

Definition A described above is considered the primary definition and will be used in the final analysis. Definition B (definition A revised, using DMD only), Definition C (definition A revised, using reactivation of disease only), and Definition D (as C but removing MRI criteria) will be also performed as a sensitivity analysis. MRI lesions or retro EDSS information are expected to be missing/not collected/not reported. Additional descriptive statistics will be provided for each of the component used in the definition to assess the validity of the criteria.

3. Subset Types of Subsequent DMDs:

- Platform injectable therapy (Interferon- β [Avonex[®], Rebif[®], Betaferon[®], Extavia[®], Plegridy[®]] or glatiramer acetate [Copaxone[®]])
- Monoclonal antibody disease modifying treatment
- Oral disease modifying treatment
- Other subsequent treatment
- Off-label treatments (drugs not approved by regulatory agencies to treat MS)
- No subsequent treatment

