14.2.2 Clinical characteristics

The clinical characteristics of study participants will be evaluated descriptively by the subgroups long-term responders and non-responders for Cohort A as per section 9.5. Clinical and demographic characteristics include gender, age, race, ethnicity, region, EDSS Score, number of relapses during last year before enrollment of parent study, prior use of DMDs, HDA Status, education, employment status, time since last IMP (years), type of first DMD after last dose of IMP, disease duration, and disease classification.

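### The primary responder definition uses a wider comparator than two secondary endpoints and the genetics endpoint name, so no single planned table shows the stated contrast

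*SAP*

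**What the plan says.** Protocol Section 3 states the aim of the second secondary objective: "To evaluate differences in clinical characteristics between long-term responders and study participants requiring alternate therapies following treatment with IMP". The endpoint beside it, repeated in SAP Section 5, defines responders as having neither reactivation nor a DMD until Year 4 or later. They are "compared to those of other study participants who started on alternate therapy less than 4 years following their last dose". The MRI endpoint and the genetics endpoint use the same comparator.

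Protocol 9.3 defines the complementary subset differently, as a DMD before 4 years or any reactivation. SAP 8.2.2 carries this forward as its primary Definition A:

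- Responder group: "Study participants not requiring DMD 4 years or later following their last dose of IMP, and who did not demonstrate any evidence of disease reactivation".
- Non-responder group: "Study participants requiring DMD less than 4 years following their last dose of IMP or who demonstrate any evidence of disease reactivation".

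The scoring table that follows makes anyone with at least one of DMD, new MRI lesion, relapse or EDSS worsening a non-responder, whatever else is missing. A responder needs all four components observed and negative.

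SAP 14.2.2 says that clinical characteristics are "evaluated descriptively by the subgroups long-term responders and non-responders for Cohort A". SAP 14.2.3 does the same for MRI in all cohorts.

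Three sensitivity definitions follow. Definition B's non-responder is "Study participants requiring DMD less than 4 years following their last dose of IMP", with nothing about reactivation. Definitions C and D use reactivation and ignore DMDs.

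**The concern.** Protocol 4.2 gives the purpose of the clinical-characteristics objective as understanding treatment sequencing, that is, who goes on to another therapy within 4 years. Reactivating without an early DMD is not the same as needing alternate therapy. It may reflect a single mild relapse, a progressive course or lack of access to treatment.

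If such participants share a column with early DMD starters, a difference in prior DMD use, HDA status, disease classification or lesion burden cannot be read as a difference between responders and those who needed another therapy. That reading is the one the endpoints promise.

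**Working it through.** No sample size, power or alpha enters here. The check is to classify every combination of DMD timing and reactivation under each definition. Inputs are the endpoint text (Protocol 3, SAP 5) and Definitions A, B and C (SAP 8.2.2). I read the DMD condition for Definition A and B responders as no DMD before 4 years, which is the Protocol 9.3 wording, and I first count reactivation only within 4 years.

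| DMD after last IMP dose | Reactivated within 4 years | Endpoint text | Definition A | Definition B | Definition C |
|---|---|---|---|---|---|
| Before 4 years | No | Comparator | Non-responder | Non-responder | Responder |
| Before 4 years | Yes | Comparator | Non-responder | Non-responder | Non-responder |
| At 4 years or later, or never | No | Responder | Responder | Responder | Responder |
| At 4 years or later, or never | Yes | **Neither** | **Non-responder** | **Responder** | **Non-responder** |

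The last row is the problem. Definition A matches the endpoint's responders but adds this row to the comparator. Definition B matches the comparator but adds this row to the responders. Definition C matches neither group, and Definition D, which also ignores DMDs, has no table in SAP 17.1 for these endpoints.

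**Planned tables.** SAP 17.1 lists 4 cohorts × 3 definitions × 2 endpoints = 24 tables in the 15.2.3 and 15.2.4 series: 8 each under A, B and C. None has both endpoint groups as its two columns. The genetics tables by responder status (15.2.11.3.1 and 15.2.11.4.1) have no Definition B version. For clinical characteristics, only the Cohort A table without a sensitivity label (15.2.3.1.1) is marked for the interim analysis.

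**The 4-year limit.** Definition A's wording sets no limit on when reactivation counts. For data after the parent study, SAP 8.2.2 explicitly checks only the MRI item against 4 years. If later relapses or EDSS worsening count, a participant with no early DMD and a first relapse after Year 4 is a responder by the endpoint text but a non-responder by Definition A. The Definition A responder column would then depart from the endpoint too.

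**Size.** Let u be the share of Definition A non-responders who have no early DMD. Let R, E and U be the percentages with some characteristic among responders, early DMD starters and reactivators without an early DMD.

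- Stated contrast: E − R.
- Definition A contrast: (1 − u)(E − R) + u(U − R).

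The two agree only if u = 0 or U = E. With purely assumed values R = 30%, E = 50% and U = 30%, the stated contrast is 20 points. Definition A gives 0.8 × 20 + 0.2 × 0 = 16 points at u = 0.2, and 0.5 × 20 + 0.5 × 0 = 10 points at u = 0.5. Setting U equal to R builds in dilution: with U above 50% the Definition A contrast would exceed 20 points. The documents give none of u, R, E or U, so neither size nor direction is known.

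**The case against.** The strongest reply is that the stated comparator is already planned. Definition B's non-responders are exactly the early DMD starters, tabulated for both secondary endpoints in all four cohorts. Under Definition A an early DMD starter is a non-responder whatever else is missing, so these are the same participants that a split of Definition A would isolate. The study is descriptive, and a reader can set the Definition A responder column beside the Definition B non-responder column. Protocol 4.2, after repeating the endpoint's responder definition, describes the data gap as started versus did not start alternate therapy within 4 years, which is the Definition B split. SAP 14.2.2 also tabulates type of first DMD, including none, and SAP 8.2.2 promises descriptive statistics for each component, so the mixture is partly visible.

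Most of this stands. A reader might infer that the stated comparator appears nowhere, and that is wrong. But the two-table reading is not pre-specified: the SAP calls Definition B a sensitivity analysis and never names that pairing as the endpoint contrast. It is unavailable in the listed genetics tables. The type-of-DMD row shows how many non-responders never took a DMD, but neither how many started late nor what these participants look like.

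A reader might also infer an undeclared SAP departure from the SAP Section 7 statement "There are no changes to the analyses planned per protocol". The documents do not support that. Protocol 9.3 already has the composite comparator and Protocol 9.4 plans the description by that subgroup, so the statement is accurate on this point.

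**Conclusion.** The point holds in a limited form. For two of three secondary endpoints and the genetics endpoint, the primary-definition comparator is wider than the one named. It adds participants who reactivated and started a DMD at 4 years or later, or never. No single planned table shows both stated groups. The secondary endpoint on EDSS 6.0 or higher is not a responder contrast and is not affected.

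The source is a conflict between Protocol Section 3 and 9.3, repeated between SAP Section 5 and 8.2.2. The membership result rests on the reading of the DMD condition stated above and on limiting reactivation to 4 years. Without that limit the mismatch is larger.

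A reader might take the pooling to dilute the contrast by a known amount. The documents do not support that: the effect depends on a share and on characteristics they do not give, and it could go either way.

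**What to change.** - In the Definition A tables (15.2.3.x.1 and 15.2.4.x.1) and the responder genetics, split non-responders into (i) a DMD started less than 4 years after the last IMP dose and (ii) reactivation without such a DMD. Amend SAP 8.2.2, 14.2.2, 14.2.3 and 14.3.6 to match.
- Name responders versus (i) as the endpoint contrast and keep the pooled non-responder column as supportive.
- State that the rule in SAP 8.2.2 and Section 14, which drops a subgroup analysis when a category holds fewer than 25% of participants, does not apply to this split. Otherwise a third category makes the whole responder analysis easier to lose. In an MRI sub-study of about 150, the threshold is 0.25 × 150 = 37.5 participants per category.
- Apply the endpoint's 4-year limit to every reactivation component of Definition A.
- Align Protocol 9.3 with Section 3. Rewording the endpoints to the composite would also remove the conflict, but would give up the treatment-sequencing purpose in Protocol 4.2.

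The cost is SAP and protocol wording plus extra table columns. DMD dates and the reactivation components are already derived. The price is a smaller comparator group and less precise descriptive estimates, mainly in the MRI sub-study.

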Subset Long-term Responder	Study participants 
 • not requiring DMD until Year 4 or later following their last dose^a of IMP, and who did not demonstrate any evidence of disease reactivation based on Investigator assessment of clinical and imaging outcomes • who started on alternate therapy (DMD) less than 4 years following their last dose^a of IMP or who demonstrate any evidence of disease reactivation based on Investigator assessment of clinical and imaging outcomes.
Subset Types of Subsequent DMDs	
 • Platform injectable therapy (Interferon-β [Avonex[®], Rebif[®], Betaferon[®], Extavia[®], Plegridy[®]] or glatiramer acetate [Copaxone[®]]) • Monoclonal antibody disease modifying treatment • Oral disease modifying treatment • Other subsequent treatment • Off-label treatments (drugs not approved by regulatory agencies to treat MS) • No subsequent treatment
Subgroup Prior Use of DMD	
 • Prior use of DMD at any time in the patient's history before enrolment into CLARITY • Complementary subgroup
Subgroup HDA for Cohort B	
 • HDA study participants • Non-HDA study participants

DMD=disease-modifying drug, HDA=high disease activity, MS=multiple sclerosis.

^a One dose is equivalent to one tablet. One course of IMP is defined as 1 year of treatment with IMP (2 treatment cycles [weeks]. A treatment cycle is defined as daily administration of IMP given consecutively over 4-5 days during a 28-day period. One treatment week is equivalent to 1 treatment cycle.

The primary and selected secondary or tertiary analyses may be repeated by these subgroups/subsets in order to evaluate the pattern of response.

It should be noted that the subgroup analyses on the subgroups' treatment courses and subsequent DMD do not support the comparison of any treatment effect as the definition of subgroups already is not independent from randomized treatment.

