Subjects who converted to CDMS according to the Poser criteria at any time during the first 96 weeks (i.e., during the double-blind period) stopped the blinded study drug and entered an open-

label maintenance period, where they were offered open-label IFN- β and underwent evaluations for safety and efficacy.

All other subjects were planned to continue their blinded treatment up to the end of the first 96 weeks double-blind period (end of Year 2).

At the end of the first 96 weeks double-blind period, McDonald MS 2005 was assessed for all subjects and treatment schedules depended on the outcome:

- Subjects who converted to McDonald MS criteria were allocated to receive open-label oral cladribine (3.5 mg/kg) administered with 1 or 2 cladribine 10 mg tablets per day over 4 to 5 days in Week 1 and Week 5 of Years 1 and 2 (total dose 3.5 mg/kg) of the extension phase.
- Subjects who did not convert McDonald MS criteria at end of Week 96 were to be followed without treatment.
- At any time during the Extension phase, open-label cladribine with 1 or 2 cladribine 10 mg tablets per day over 4 to 5 days in Week 1 and Week 5 of Years 1 and 2 (total dose 3.5 mg/kg) if conversion to McDonald MS criteria or IFN- β (if conversion to CDMS) may have been used following the rule above.

The ORACLE MS was terminated earlier than planned in October 2011. No further dosing of blinded study medication or open-label cladribine was allowed (open-label IFN- β was offered for subjects who converted to McDonald MS). Subjects were to complete the end of trial visit assessments after a safety follow-up period of 24 weeks from the time of last dose of blinded study medication or open label cladribine.

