Subsequent DMD groups will be identified using a DMD medication lookup list provided by the coding team and reviewed by the medical team. This DMD list will be looked vs all medications reported in prior/concomitant medications, Physician Sequential Treatment Decision eCRF page question 8 in CLASSIC and parent study data. The first subsequent DMD after last dose of IMP will be used to define the subset.

4. Subgroup Prior Use of DMD for cohort B:

- Prior Use of DMD at any time in the patient's history before enrolment into CLARITY
- Complementary subgroup

Prior use of DMD will be identified using same approach described for subsequent DMD using parent study data.

5. Subgroup High Disease Activity for Cohort B:

[figure not shown]
The definition of HDA will be similar to regulatory submission, programs from EMA CSE, will include patients from CLARITY study, and subgroups will be identified using parent study data.

HDA is defined by:

- a) Patients with ≥ 1 relapse during the year prior to parent study entry and ≥ 1 T1 Gd+ lesions or ≥ 9 T2 lesions, while on therapy with other DMDs, OR
- b) Patients with ≥ 2 relapses during the year prior to parent study entry, regardless of prior disease modifying drugs (DMD) use.

Non-HDA is the complementary group.

Table 1: High Disease Activity Definition details

Patients in the previous year while on DMD therapy
	
DMD are medications with preferred term defined in section 12 of the iAP.
 
If more than 1 DMD is used, only last DMD (the closest to Parent Study Day 1 [PSD1]) is considered. Collected start/end date of prior DMD is used to compute prior DMD treatment duration. If end date after PSD1, duration is truncated to PSD1-1. When start/end date are partial (day or month or year missing), imputation rule as described in section 9.5 of the iAP is followed.

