11.2 Medical History

The medical history will be summarized from the “Medical History details” eCRF page, using MedDRA, preferred term as event category and system organ class (SOC) body term as Body System category. Each participant will be counted only once within each PT or SOC.

Listing will also be provided.

12 Previous or Concomitant Medications/Procedures

Previous or concomitant medication will be presented based on FAS analysis set for Cohort A and will be presented by ATC and Preferred Name, per parent study exposed group and total. Listing will also be provided.

Previous and concomitant medications are medications, other than parent study medications (i.e. cladribine or placebo), which are taken by patients any time on-trial before or on or after CLASSIC Study Visit 1.

Handling of missing or partial dates are critical for medications identified as DMD that will determine timing of DMD in responders/non-responders and prior DMD use variables. All missing/incomplete dates will be imputed as described in Section 9.5.

Medications in CLASSIC

Medications in CLASSIC are medications which are taken by subjects at any time after (>) the end of the parent study day. Reporting will be done for Cohort A, FAS analysis set.

Disease modifying drugs in CLASSIC

MS-DMDs drugs will be identified using lookup list against all concomitant medication reported as well as eCRF dedicated question. Coding group will provide initial list using drug code, ATC and other elements for the medical team to review and approve prior to data base lock. Final list will be similar to table 3 below and will be standalone document (Appendix 17.2). First, Second, third and any subsequent DMD after first and last dose of Cladribine will also be reported descriptively. Each one will be identified based on the date of the DMD in ascending order since the date of first dose of IMP. First subsequent DMD will be reported by DMD type and ATC and second and third subsequent DMDs will be reported by DMD type only. First subsequent DMD will also be summarized by type, ATC and Medication Name. Patterns of DMD switches will be described also and provided only for the final analysis. Reporting will be done for all cohort, FAS analysis set.

A listing of subsequent DMDs after last IMP dose will be provided for subjects with repeating DMD types.

Table 4: List of MS-DMD

Drug Name	ATCs	SDGs (Standard Drug Groupings)

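### The long-term responder rule does not name parent-study data as a source for DMD dates, so a DMD confined to the parent trial has no guaranteed source; the exposure is mainly in sensitivity Definition B.

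*SAP*

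**What the plan says.** In SAP 8.2.2, item 2a, a responder must be free of DMD and of disease reactivation. The window ends at last IMP dose + 4*365.25 days. For the DMD component, the computation rules name the prior/concomitant medication page and the physician treatment-decision "eCRF page question 8 and 9 to be used to identify the date of the DMD received". Parent-study data are not mentioned.

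The other three components (relapse, MRI lesions, EDSS worsening) "will be identified utilizing dates in parent studies for the period between last dose of IMP and end of parent study"; CLASSIC pages are used after that.

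Item 3 of the same section, the subset by type of subsequent DMD, takes the first DMD after the last IMP dose. It applies a lookup list to the prior/concomitant medications and to "Physician Sequential Treatment Decision eCRF page question 8 in CLASSIC and parent study data".

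Two further places matter:

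- SAP 6.2: ORACLE subjects who converted to CDMS in the double-blind period stopped blinded drug and entered an open-"label maintenance period, where they were offered open-label" interferon beta. At early termination, interferon was also offered to McDonald converters.
- SAP 12: "Medications in CLASSIC are medications which are taken by subjects at any time after (>) the end of the parent study day".

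On wording, the SAP describes the responder as "Study participants not requiring DMD 4 years or later following their last dose of IMP", whereas Protocol 9.3 has "not requiring DMD until Year 4 or later following their last" dose.

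**The concern.** The plan looks for the same fact, a DMD after the last IMP dose, in two different ways within one section. Followed as written, a patient given interferon only during ORACLE could be a platform-injectable patient in the DMD subset and DMD-free in the responder subset.

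Responder status defines two secondary comparisons (SAP 14.2.2 and 14.2.3), the HDA comparison (14.3.5) and the genetic association analysis (14.3.6). A missed in-trial DMD moves a non-responder into the responder group or into the not-determined group. Because ORACLE had interferon in its design, the loss could differ between Cohort D and Cohort B.

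**Working it through.** **1. Sources side by side (last IMP dose to end of parent study)**

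| Item in SAP 8.2.2 | CLASSIC pages | Parent-study data |
|---|---|---|
| Relapse, MRI, EDSS in the responder rule | used for the later period | named |
| First subsequent DMD, subset 3 | named | named |
| DMD in the responder rule | named | not named |

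Only the last row lacks the parent-study source.

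**2. How much of the window lies inside a parent trial**

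The window is 4 × 365.25 = 1461 days, or 1461/7 = 208.7 weeks.

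- ORACLE, 24-week safety follow-up after last dose (SAP 6.2): 24/208.7 = 11.5%.
- CLARITY, to week 96: 96 − 53 = 43 weeks; 43/208.7 = 20.6%.
- CLARITY-EXT, to week 96 plus 24 weeks of follow-up: 120 − 53 = 67 weeks; 67/208.7 = 32.1%.

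The last two assume 48-week treatment years with the last dose in Week 5 of Year 2, about study week 53. An ORACLE converter whose last dose was in Week 5 or Week 13 of Year 1, and who was followed to week 96, would have 91 weeks (43.6%) or 83 weeks (39.8%) in-trial. All of these are shares of elapsed time. None is a misclassification rate.

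**3. Effect of a missed DMD on classification**

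Take a patient with a true in-trial DMD inside the window, not found and coded N. The correct class is non-responder.

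- *Definition B* uses DMD alone, so the patient is a responder whatever the other data show.
- *Definition A*, using the SAP decision table: relapse, MRI and EDSS can each be Yes, No or missing, giving 3³ = 27 patterns. Patterns without any Yes number 2³ = 8. The other 27 − 8 = 19 still give non-responder. Of the 8, one (all No) gives responder and 7 (at least one missing) give ND.
- With nothing missing, Definition A errs in 1 of 2³ = 8 patterns.

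These are counts of patterns, not probabilities. The ND route still deserves attention, because the SAP expects MRI or retrospective EDSS information to be missing.

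**4. Where it shows**

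Tables in Appendix 17.1 titled for Definition B: primary endpoint 4, EDSS of 6.0 or higher 4, clinical characteristics 4, MRI characteristics 4, one per cohort each time. Total 16.

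**5. Illustration for Definition B (assumed values)**

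If the true responder rate is R and a share u of all patients had only an uncaptured in-trial DMD, the apparent rate is R + u, and u/(R + u) of labelled responders are wrong. For R from 30% to 70% and u from 2% to 10%, the rate rises by 2 to 10 points. The wrongly labelled share runs from 0.02/0.72 = 2.8% to 0.10/0.40 = 25%. The documents give no value for R or u.

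**The case against.** The strongest reply is that the rule says which pages to use, not that nothing else may be used, and that those pages may reach back into the parent trial. Protocol 8.1.1.4 has the physician questions record, by chart review, the first treatment after the first cladribine course, a starting point inside the parent trial. SAP 12 also opens with a definition of previous and concomitant medications that has no lower bound at the end of the parent study, and it links DMD dates to responder status. The narrower definition follows for a specific report. This stands: a reader might infer that in-trial DMDs are excluded, and the documents do not say so. Nor do they show capture. The wording of questions 8 and 9 is not given, and Protocol 6.5 and 8.1.1.4 frame them around Cladribine Tablets, which leaves placebo patients unclear.

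A reader might also infer that ORACLE interferon patients become responders under the primary definition. Mostly they would not. Double-blind-period interferon followed CDMS conversion, the relapse would normally be in the parent data, and one Yes is enough for non-responder. What remains is, for example, interferon offered at termination to someone whose McDonald conversion preceded the last open-label cladribine dose, with no later reactivation.

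It is also true that Definition B is a sensitivity analysis, that all subgroup work is descriptive, and that the SAP plans descriptive statistics for each component. That limits the weight of the point but does not remove the inconsistency. A distortion of Cohort D against Cohort B is possible, but without counts it is not shown.

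**Conclusion.** The gap is real and narrow. The responder rule omits a source that the same section uses for the other three components and for the DMD subset. DMDs confined to the parent trial may be missed; that they are missed cannot be established from the documents.

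Definition B carries most of the exposure, because nothing else in it can correct a missed DMD. Under Definition A, the error is limited to patients with no recorded relapse, new lesion or EDSS worsening: a false responder if those components are complete, ND if any is missing. A missed DMD must also have stopped before the parent study ended, or gone unrecorded on the CLASSIC pages. The number affected is unknown here and can be counted from parent datasets that SAP 6.3 already brings into the analysis.

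The wording difference is secondary. Read literally, the SAP phrase places a first DMD at year 6 in neither group and a DMD taken only in year 2 in both. A reader might take this as a second fault, but SAP Section 5 states the full rule, item 2a gives a single cut-off date, and the non-responder wording refers to less than four years. It needs tidying, not a new rule.

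**What to change.** - In SAP 8.2.2, for Definitions A and B, identify the first DMD after the last IMP dose with the method of item 3: the DMD lookup list applied to the CLASSIC pages and to parent-study medication and exposure data, with ORACLE open-label interferon named explicitly.
- Add a programmed check that no patient coded N for DMD required has a subsequent DMD dated before LDIMP + 4*365.25 days. Report how many patients change class, by cohort.
- State in SAP 12 that its definition of medications in CLASSIC does not limit the responder derivation.
- Restore the word *until* in the responder wording of item 2a and Definition B, to agree with Protocol 9.3 and SAP Section 5. State that DMD required means before the cut-off date.

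The cost is SAP wording and reuse of a lookup already planned, with no new data collection. The responder rate may fall slightly.
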